8.1 Screening Procedures (-30 to -1)

Recruitment into this study will initially involve [REDACTED] recruitment procedures and general screening, during which volunteers will voluntarily consent to and sign an ERB/IRB approved Volunteer Consent Form (VCF) and Privacy Consent Form (PCF).

An ICF specific to this study will be signed by all subjects prior to any study specific procedures occurring.

Screening will include the following procedures either at the screening visit or at Period 1 check-in:

- Screening evaluations (Screening consent: Inclusion/Exclusion Criteria);
- Medical and medication history;
- Demographic data collection and height and weight measurements, as well as BMI calculation;
- Vital signs (blood pressure, pulse rate, respiration rate, and temperature) will be measured after the subjects have been resting for at least 3 minutes in a sitting position;
- 12-lead ECG will be recorded after the subjects have been resting in a semi-recumbent or supine position;
- Blood and urine sample collection.

Table 7. Blood and Urine Tests Performed at Screening

Biochemistry	Hematology	Urinalysis
Random glucose Total bilirubin BUN Creatinine Alkaline phosphatase Calcium LD AST (SGOT) ALT (SGPT) Serum electrolytes (sodium, potassium, and chloride) GGT FSH LH Note: FSH and LH will be tested only in female subjects with a menstrual history consistent with being postmenopausal.	CBC with differential: 
 • WBC count with differential • Hemoglobin • Hematocrit • RBC count and indices Platelet count	Specific gravity pH Leukocytes Nitrites Protein Glucose Ketones Blood Microscopic examination Note: microscopic examination will only be performed when any of the following urinalysis tests are reported abnormal (i.e., outside of normal ranges): leukocyte, nitrite, protein, and/or blood. The microscopic examination will be conducted on the same urine sample as the abnormal urinalysis test.
Serology	Drugs of Abuse	Immunohematology
HIV-1 and HIV-2 antibodies HCV antibody HBsAg	Amphetamines Barbiturates Benzodiazepines Cannabinoids Cocaine Methadone Opiates Phencyclidine Tricyclic antidepressants	Serum β -HCG (females only)

Abbreviations: ALT (SGPT) = alanine aminotransferase; AST (SGOT) = aspartate aminotransferase; β -HCG = beta-human chorionic gonadotropin; BUN = blood urea nitrogen; CBC = complete blood count; FSH = follicle-stimulating hormone; GGT = gamma glutamyl transpeptidase; HBsAg = hepatitis B surface antigen; HCV = hepatitis C virus; HIV = human immunodeficiency virus; LD = Lactate dehydrogenase; LH = luteinizing hormone; RBC = red blood cell; WBC = white blood cell.

8.2 Test/ Procedures at check-in

Check-in of Period 1

- ICF signature for the study (if not done before);
- Medical and medication history;
- Any outstanding screening procedure that is not completed, or needs to be repeated;
- Complete physical examination including assessments of the following: head, eyes, ears, nose, throat (HEENT), neck, chest, lungs, abdomen, musculoskeletal, dermatological, cardiovascular/peripheral vascular, and general neurological examination;
- Temperature measurement;

- Weight;
- Urine drugs of abuse (amphetamines, barbiturates, benzodiazepines, cannabinoids, cocaine, methadone, opiates, phencyclidine, and tricyclic antidepressants);
- Urine β -HCG and serum β -HCG (females only);
- Breath alcohol;
- Confirm inclusion/exclusion criteria.

Check-in of Period 2, 3, 4

- Temperature measurement;
- Urine drugs of abuse (amphetamines, barbiturates, benzodiazepines, cannabinoids, cocaine, methadone, opiates, phencyclidine, and tricyclic antidepressants);
- Urine β -HCG and serum β -HCG (females only);
- Breath alcohol;
- Medical and medication history.

Clinical study personnel reserve the right to conduct additional testing (e.g., breath alcohol test, diagnostic imaging) at any time throughout the study.

8.3 On-study procedures:

- Temperature measurement daily;
- Vital signs (blood pressure and pulse rate) will be measured after the subjects have been resting for at least 3 minutes in a sitting position: before dosing (0-hour), and at 4 and 6 hours post-dose;
- 12-lead ECG will be recorded after the subjects have been resting in a semi-recumbent or supine position: before dosing (0-hour), at 4 and 6 hours post-dose;
- Study treatment administration; and
- Pharmacokinetic Blood Sample Collection: -1, -0.5, pre-dose (0), and 0.333, 0.667, 1, 1.5, 2, 2.5, 3, 3.5, 4, 4.5, 5, 5.5, 6, 8, 12, 16, and 24 hours post-dose.

Table 8. Time Windows for PK Blood Samples

Day	Time point	Time window
1	-1 hour, and -0.5 hour	± 5 minutes
	Pre-dose (0-hour)	Within 5 minutes
	0.333, 0.667, 1, 1.5, 2, 2.5, 3, 3.5, 4, 4.5, 5, 5.5, and 6 hours	± 1 minute
	8, 12, and 16 hours	± 3 minutes

2	24 hours	±3 minutes
---	----------	------------

Samples collected outside the acceptable window will not be considered as protocol deviations, but rather the actual clock time of each sample collection will be recorded.

8.4 End of study procedures

End-of-study for each subject is defined as the last study specific procedure in the last period of the study or the last study specific procedure prior to the discontinuation of a subject from the study.

End-of-study will include the following procedures:

- A brief physical examination including assessments of the following: HEENT, chest, lungs, abdomen, dermatological, cardiovascular/peripheral vascular, and areas of note elicited from the subject;
- Vital signs (blood pressure, pulse rate, respiration rate, and temperature) will be measured after the subjects have been resting for at least 3 minutes in a sitting position;
- 12-lead ECG will be recorded after the subjects have been resting in a semi-recumbent or supine position; and
- Blood and urine sample collection.

Table 9. Blood and Urine Tests Performed at End of Study

Biochemistry	Hematology	Urinalysis
Random glucose Total bilirubin BUN Creatinine Alkaline phosphatase Calcium LD AST (SGOT) ALT (SGPT) GGT Serum electrolytes (sodium, potassium, and chloride)	CBC with differential: 
• WBC count with differential• Hemoglobin• Hematocrit• RBC count and indices Platelet count	Specific gravity pH Leukocytes Nitrites Protein Glucose Ketones Blood Microscopic examination Note: microscopic examination will only be performed when any of the following urinalysis tests are reported abnormal (i.e., outside of normal ranges): leukocyte, nitrite, protein, and/or blood. The microscopic examination will be conducted on the same urine sample as the abnormal urinalysis test.
Immunohematology		Serum β-HCG (females only)

Abbreviations: ALT (SGPT) = alanine aminotransferase; AST (SGOT) = aspartate aminotransferase; β-HCG = beta-human chorionic gonadotropin; BUN = blood urea nitrogen; CBC = complete blood count; GGT = gamma glutamyl transpeptidase; LD = Lactate dehydrogenase; RBC = red blood cell; WBC = white blood cell.

For subjects who are removed or withdrawn from the study, end-of-study procedures will still be conducted. Subjects who do not return for end-of-study procedures will be considered lost-to-follow-up.

If a subject is not able to repeat any end-of-study tests at the clinic, they may repeat the test with their local healthcare provider/laboratory. All external results will be reviewed by the Investigator.

8.5 Pharmacokinetic Assessments

8.5.1 Pharmacokinetic Blood Sample Collection and Processing

In each period, blood samples for PK analysis will be collected via an intravenous catheter or by direct venipuncture.

The PK Scientists will be contacted to evaluate the subject's continued participation in the study if any of the following incidents occur in any period:

- The 24-hour scheduled blood draw is missed; or
- At least two consecutively scheduled blood draws are missed.

The impact of these incidents on the estimation of PK parameters will be made as close to the time of occurrence as possible.

The planned volume of blood to be collected for this study, including that collected for eligibility and safety purposes, should not exceed 500 mL. Additional tests or blood draws could be performed, if deemed required by the Investigator or study staff.

Procedures for collection, processing, and shipping of PK blood samples will be detailed in a laboratory manual.

Plasma concentrations of the study treatment will be determined using a validated analytical method. Details of the analytical method will be provided in a separate document.

8.6 Safety and Tolerability Assessments

Subjects will be monitored throughout the study by the clinical staff for AEs. Adequate medical surveillance will be assured during the confinement period. The Investigator will be on-site until 4 hours after the last subject is dosed and on call throughout the study. If necessary, the Investigator or designee at the clinical site or a healthcare professional in a nearby hospital will administer treatment for any AE(s). A crash cart or emergency bag containing the necessary rescue material and appropriate medications will be available in the clinic to allow rapid intervention in case of emergency.

Safety parameters will be assessed by the Investigator or designee, using the clinical site acceptance ranges as suggested guidelines in making the medical assessment.

For eligibility purposes, abnormal vital signs measurements or clinical laboratory test results may be repeated up to two times if an abnormal result is observed at the initial reading. Moreover, abnormalities found in the ECG may need to be confirmed by repeated measurements. In the event that the participation of a subject in the study is delayed and some screening procedures had been performed outside of the prescribed screening window, outdated screening procedures can be repeated.

Safety assessments scheduled during the study will be repeated according to the clinical site SOPs or upon request from the Investigator or designee. Any abnormal repeated measurement will be evaluated and repeated, if judged necessary. Further action may be taken upon the Investigator or designee's request.

8.7 Adverse Events

8.7.1 Definition of Adverse Event

An AE is defined as any untoward medical occurrence in a patient or clinical trial subject administered a pharmaceutical product and which does not necessarily have a causal relationship with the treatment. An AE can, therefore, be any unfavorable and unintended sign (including an abnormal laboratory finding, for example), symptom, or disease temporally associated with the use of a medicinal (investigational) product, whether or not considered related to the medicinal (investigational) product.

8.7.2 Recording of Adverse Events

AEs will be recorded and evaluated for their seriousness, severity, and relationship to the study treatment. AEs will be collected and documented from the time of signing the ICF and throughout the study. AEs will be followed-up until complete resolution, or until the Investigator or designee judges safe to discontinue follow-up. The severity of AEs and relationship to the study treatment will be classified according to the sections below.

AEs will be classified according to the Medical Dictionary for Regulatory Activities (MedDRA) and reported with respect to severity, duration, relationship to study treatment(s) and action taken.

IRB Reviewed - June 12, 2024

8.7.3 Assessment of Severity

The severity of AEs will be described and documented using the following definitions:

Table 10. Severity of Adverse Events

Severity	Description
Mild	Awareness of signs and symptoms, but are easily tolerated; are of minor irritant type; causing no limitations of usual activities. Signs or symptoms may require minor action.
Moderate	Discomfort severe enough to cause some limitations of usual activities and may require action.
Severe	Incapacitating with inability to carry out usual activities or significantly affects clinical status, and requires specific action and/or medical attention.

8.7.4 Assessment of Relationship to Study Treatment

Each AE must be classified based on medical judgment and according to the following relationship categories: probable, possible, remote/unlikely, and unrelated. The definitions for the relationship categories are as follows:

Table 11. Adverse Event Relationship Categories

Category	Description
[Related] Probable (must have first three points)	This category applies to AEs that are considered, with a high degree of certainty, to be related to the investigational product. An AE may be considered probable, if: 
1. It follows a reasonable temporal sequence from the administration of the study treatment.2. It cannot be reasonably explained by the known characteristics of the participant's clinical state, environmental or toxic factors or other modes of therapy administered to the participant.3. It disappears or decreases on cessation or reduction in dose (there are important exceptions when an AE does not disappear upon discontinuation of the study treatment, yet relatedness clearly exists; e.g. (1) bone marrow depression, (2) tardive dyskinesias).4. It follows a known pattern of response to the suspected study treatment.5. It reappears upon re-challenge.
[Related] Possible (must have first two points)	This category applies to AEs in which the connection with the investigational product administration appears unlikely but cannot be ruled out with certainty. An AE may be considered possible if, or when: 
1. It follows a reasonable temporal sequence from the administration of the study treatment.2. It may have been produced by the participant's clinical state, environmental or toxic factors, or other modes of therapy administered to the participant.3. It follows a known pattern of response to the suspected study treatment.

Remote/Unlikely (must have first two points)	In general, this category is applicable to an AE that meets the following criteria: 
1. It does not follow a reasonable temporal sequence from the administration of the study treatment.2. It may readily have been produced by the participant's clinical state, environmental or toxic factors, or other modes of therapy administered to the participant.3. It does not follow a known pattern of response to the suspected study treatment.4. It does not reappear or worsen when the study treatment is re-administered.
Unrelated	This category is applicable to AEs that are judged to be clearly and incontrovertibly due only to extraneous causes (disease, environment, etc.), and do not meet the criteria for medication relationship listed under remote/unlikely, possible, or probable.

8.7.5 Definition of Serious Adverse Event

A serious adverse event (SAE) is defined as any untoward medical occurrence that, at any dose:

- Results in death;
- Is life-threatening (i.e., its occurrence places the subject at immediate risk of death);
- Requires inpatient hospitalization or prolongation of existing hospitalization;
- Results in persistent or significant disability/incapacity;
- Is a congenital anomaly/birth defect;
- Is otherwise considered to be an important medical event that may not be immediately life-threatening or result in death or hospitalization but may jeopardize the patient or may require intervention to prevent one of the other outcomes listed in the definition above. Medical and scientific judgement should be exercised in deciding whether an event should be considered as an Important Medical Event. Examples of such medical events include:
 - Allergic bronchospasm requiring intensive treatment in an emergency room or at home;
 - Blood dyscrasias or convulsions that do not result in hospitalization;
 - Development of drug dependency or drug abuse.

8.7.6 Reporting of Adverse Events

8.7.6.1 Serious Adverse Event Reporting to the Sponsor

Any SAE will be reported to the Sponsor (or representative) within 24 hours of learning of the event. The notification must be directed to:

SAE contact information:

8.7.6.2 Serious Adverse Event Reporting to the IEC and Regulatory Agency(ies)

It is the responsibility of the clinical site to report suspected, unexpected, serious adverse reactions (SUSARs) to the IEC responsible for the study per their policies. Report of fatal or life-threatening SUSARs must be made as soon as possible, but no later than 7 calendar days after first knowledge of the event. Report of SUSARs that are neither fatal nor life-threatening must be made as soon as possible, but no later than 15 calendar days after first knowledge of the event.

The Sponsor (or representative) is responsible for notifying the regulatory agency(ies) of SUSARs observed during the study conduct per their regulations, as soon as possible but no later than 7 calendar days after becoming aware of the information when fatal or life-threatening, or 15 calendar days when neither fatal nor life-threatening. The Sponsor (or representative) is responsible to comply with any other applicable regulatory requirement(s) related to the reporting of SAE to other regulatory authority(ies).

8.7.7 Pregnancy

In the event a dosed female participant or the female partner of a dosed male participant (i.e., has received at least one dose of the investigational product) becomes pregnant during or shortly after participation in the study, this pregnancy will be reported to the Sponsor (or representative) within 24 hours of first knowledge of the event. Any subject who becomes pregnant during the study will be immediately withdrawn. Follow-up information regarding the course and outcome of the pregnancy will be documented (after obtaining the consent of the female partner) as per site's SOP. If the outcome of the pregnancy meets the criteria of reportable event, reporting of the event to the IEC responsible for the study and/or to applicable regulatory agency(ies) will be performed as per site's SOP.

8.8 Premature Termination of the Study

The study may be prematurely terminated by the Investigator following consultation with the Sponsor, by the Sponsor or by the regulatory authorities. Following a decision to discontinue the trial, the Investigator will promptly inform the active study subjects and the IEC responsible for this trial, stating the reasons for discontinuation of the study. It is the responsibility of the Sponsor (or representative) to report the premature termination of the study to the regulatory authority(ies), when required by the applicable regulatory requirement(s).

9. Statistical Analyses

For all PK analysis, all concentrations below the limit of quantification will be set to 0.

Samples with invalid concentration (due to bioanalytical or clinical issue) will be replaced by “0.00” when it occurs prior to dosing for PK parameters calculation. Otherwise, they will be set to missing for tabulation, graphical representation, and calculation purposes if it occurs after dosing.

The primary objective of this study is to evaluate the relative bioavailability of a new oral suspension formulation. Since this study is exploratory, no formal hypothesis testing is defined.

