1.2.2 Rationale for Baseline Correction

Sapropterin is an endogenous compound and should therefore be analyzed both with and without baseline correction. Therefore, for baseline correction, for each subject and treatment period, the baseline value will be defined as the mean of the -1 hour, -0.5 hour, and pre-dose (0) samples obtained before dosing, for that same subject and period.

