9.1.3 Pharmacokinetic Statistical Population

The PK statistical population will include all subject's data from the PK population who complete at least two periods, where a statistical comparison can be made for at least one PK parameter and who have not experienced any protocol deviations or other circumstances to exclude the subject from the PK statistical analysis.

Individual period data will be excluded if a baseline-corrected pre-dose concentration (at time 0-hour) greater than 5% of the corresponding C_{max} is observed for a subject.

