9.2 Pharmacokinetic Parameters

The actual post-dose sample collection times will be used in the PK analysis.

The following PK parameters and observations will be calculated based on data from the PK population
[REDACTED]
later) for ba

- AUC_{0-t} : Area under the concentration-time curve from time zero until the last observed concentration, as calculated by the linear up/log down variant of the trapezoidal method.

- $AUC_{0-\infty}$: Area under the concentration-time curve from time zero to infinity (extrapolated)
- Residual area: Percentage of $AUC_{0-\infty}$ due to extrapolation from the time of the last observed concentration to infinity, calculated as $[1 - (AUC_{0-t}/AUC_{0-\infty})] \times 100$
- C_{\max} : Maximal observed concentration
- T_{\max} : Time when the maximal concentration is observed
- T_{lag} : Time of observation prior to the first observation with a measurable (non-zero) concentration.
- $T_{1/2 \text{ el}}$: Terminal elimination half-life
- K_{el} : Terminal elimination rate constant
- Cl/F : Apparent clearance
- V_z/F : Apparent volume of distribution
- R^2 : Coefficient of determination obtained from regression analysis

Additional PK parameters may be calculated. K_{el} , $T_{1/2 \text{ el}}$, and $AUC_{0-\infty}$ parameters will not be estimated for concentration-time profiles where the terminal linear phase is not clearly defined.

Sapropterin is an endogenous compound and therefore, should be analyzed both with and without baseline correction. Pharmacokinetic parameters will be calculated based on uncorrected plasma concentrations and baseline-corrected plasma concentrations, as appropriate. Baseline corrected for sapropterin will be performed by calculating the mean plasma pre-dose levels for each subject within each period of the study using the measured concentrations at the -1, -0.5, and the 0-hour time points. The mean of these pre-dose values will be the *baseline* for that period for that subject. The baseline value will be subtracted from all subsequent measured concentrations (including 0-hour) for the same subject within the same period. Negative baseline adjusted levels will be set to zero before the PK analysis. No adjustment of the pre-dose or post-dose concentrations will be performed for the baseline uncorrected data.

IRB Reviewed - June 12, 2024

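### Section 9 turns invalid pre-dose concentrations into 0.00 for an endogenous analyte, and no visible text keeps that zero out of the baseline mean (minor)

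*Combined protocol and SAP*

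**What the plan says.** Two sets of rules meet here.

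- **Invalid samples (section 9, opening paragraphs).** An invalid concentration "will be replaced by “0.00” when it occurs prior to dosing for PK parameters calculation". For post-dose samples the rule differs: "Otherwise, they will be set to missing for tabulation, graphical representation, and calculation purposes if it occurs after dosing". A separate sentence sets values below the quantification limit to 0; that is not at issue.
- **Baseline (sections 1.2.2 and 9.2).** In 1.2.2, "the baseline value will be defined as the mean of the -1 hour, -0.5 hour, and pre-dose (0) samples obtained before dosing", per subject and period. In 9.2 the baseline is obtained by "calculating the mean plasma pre-dose levels for each subject within each period of the study using the measured concentrations" at the same three times. Then: "The baseline value will be subtracted from all subsequent measured concentrations (including 0-hour) for the same subject within the same period". And: "Negative baseline adjusted levels will be set to zero before the PK analysis".

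Two further provisions depend on these values. AUC0-t in 9.2 is the "Area under the concentration-time curve from time zero until the last observed concentration, as calculated by the linear up/log down" trapezoidal variant, so it uses nothing before time zero. Section 9.1.3 says: "Individual period data will be excluded if a baseline-corrected pre-dose concentration (at time 0-hour) greater than 5" percent of that profile's Cmax.

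Section 3 lists both uncorrected and baseline-corrected AUC0-t, AUC0-inf and Cmax as primary endpoints. Section 1.1 gives the endogenous level as about 3–10 ng/mL.

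**The concern.** Zero is a sensible stand-in for a pre-dose value when the drug is absent before dosing. For an endogenous compound it is a false value. If it enters a three-sample mean, the baseline for that period is too low, and every corrected concentration in the profile is too high by the same amount.

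The -1 h and -0.5 h samples make the question hard to set aside. AUC starts at time zero and a zero cannot be Cmax, so these samples reach the primary endpoints only through the baseline. For them, the substitution rule either distorts the baseline or does nothing. They are 16 × 4 × 2 = 128 of the 16 × 4 × 3 = 192 scheduled pre-dose samples. Two programmers could implement the text differently and each defend the choice.

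**Working it through.** The plan states no figure that depends on this rule, so there is nothing to reproduce. The steps below give the effect if the zero is averaged in.

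**Inputs.** True baseline b = 3 to 10 ng/mL (section 1.1). Table 2 intact-tablet means: fed Cmax 105 ng/mL; AUC0-t 635 (fed) and 474 (fasting) ng·h/mL. Sixteen subjects (section 5.1). Assumption: pre-dose levels within a period are similar.

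**Offset from one false zero.** Baseline used = (b + b + 0)/3 = 2b/3. Each corrected concentration rises by b/3: 1.00 ng/mL at b = 3 and 3.33 at b = 10. Two false zeros double this. With three, nothing is subtracted.

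**Cmax.** 1.00/105 = 0.95%; 3.33/105 = 3.17%.

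**AUC0-t, concentrations at or above the true baseline to 24 h.** Added area = 24 × b/3 = 24 to 80 ng·h/mL.

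| Scale | b = 3 | b = 10 |
|---|---|---|
| Fed, 635 | 3.8% | 12.6% |
| Fasting, 474 | 5.1% | 16.9% |

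If the last quantifiable time is 12 h, halve these. The dissolved/fasting row of Table 2 is not used as a scale, because no treatment here is dissolved product given fasted.

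**Check on an illustrative profile.** Linear rise to 105 at 4.5 h, decline at 0.27/h, protocol sampling times, linear up/log down, last three points for the terminal slope. AUC0-t rises by 26.8 (b = 3) and 85.8 (b = 10), slightly more than 24 and 80 because of the log-down rule. AUC0-inf rises by 33 and 116, that is 5.3% and 18.6% of this profile. The leftover offset flattens the terminal slope: half-life goes from 2.6 h to 3.7 h and 5.8 h.

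**Effect on a treatment's geometric mean, one affected profile in 16.**
- AUC0-t fed: 1.038^(1/16) − 1 = 0.23%; 1.126^(1/16) − 1 = 0.74%.
- AUC0-t fasting: 1.051^(1/16) − 1 = 0.31%; 1.169^(1/16) − 1 = 0.98%.
- Cmax fed: 1.0095^(1/16) − 1 = 0.06%; 1.0317^(1/16) − 1 = 0.20%.

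**The 5% rule in 9.1.3.** With a false zero at -1 h or -0.5 h and a valid 0-hour sample, the corrected 0-hour value is b − 2b/3 = b/3. It exceeds 5% of Cmax when the computed corrected Cmax is below (b/3)/0.05 = 6.67b: 20 ng/mL at b = 3 and 66.7 at b = 10. At a true corrected Cmax of 105 and b = 10, the limit is 0.05 × 108.3 = 5.42, above 3.33, so the period stays in. With two false zeros the thresholds double to 40 and 133.

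**Uncorrected AUC.** It changes only if the 0-hour sample is the invalid one: b × 0.333/2 = 0.5 to 1.7 ng·h/mL lost.

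**The case against.** The best defence is textual. Section 9.2 is the operative rule and speaks of measured concentrations; a substituted 0.00 is not measured. Section 9 confines the zero to the calculation of PK parameters, and 9.2 places the baseline adjustment ahead of the PK analysis. On that reading the zero only supplies a start point for AUC, where it is about right on the corrected scale. A general sentence about pre-dose samples need not affect all of them. Part of 9.2 is also redacted and may settle the matter.

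This reading is plausible, and it rules out a stronger inference: a reader might conclude that the plan will average false zeros into the baseline. The documents do not show that. But the defence does not close the question either. Section 1.2.2 refers only to samples obtained before dosing, the section 9 rule covers every pre-dose sample, and no visible sentence connects the two.

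Three other objections stand. The 3–10 ng/mL range comes from a statement on in vitro protein binding, not from pre-dose levels measured in this design. The rate of invalid samples is not given. And the study is exploratory, with no formal hypothesis test.

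A reader might also object that an invalid 0-hour sample set to zero passes the 5% check automatically: it goes negative after subtraction and is reset to zero. That is so, but it alters no outcome. If the value were left out, there would be nothing to check and no visible rule would exclude the period.

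**Conclusion.** The concern holds as a minor one. A stated rule unsuited to an endogenous analyte can, on one fair reading, distort baseline-corrected primary endpoints. Per affected profile, one invalid sample adds about 1.0–3.2% to Cmax (fed) and about 3.8–12.6% (fed) or 5.1–16.9% (fasting) to AUC0-t, with more possible for AUC0-inf. Across 16 subjects, one such profile moves a geometric mean AUC0-t by about 1% or less.

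These sizes rest on a stable pre-dose level of 3–10 ng/mL, concentrations at or above the true baseline to 24 h, and tablet means as the scale. Table 2 does not say whether its values are baseline-corrected. The AUC figures are approximate and should not be read as upper bounds.

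A reader might infer bias towards one product or condition. Nothing in the documents suggests that invalid samples cluster in one treatment, so added noise is what to expect. False exclusion under the 5% rule is possible but, with one invalid sample, is confined to profiles with computed corrected Cmax below about 20 ng/mL (b = 3) or 67 ng/mL (b = 10).

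**What to change.** - **Section 9:** set invalid pre-dose concentrations to missing for the baseline calculation, as is already done for invalid post-dose values.
- **Sections 1.2.2 and 9.2:** use one definition, the mean of the valid pre-dose samples of that subject and period. State that a period with no valid pre-dose sample is left out of the baseline-corrected analysis.
- **AUC start point:** an invalid 0-hour value may still be imputed, as zero on the corrected scale and as the period's baseline mean on the uncorrected scale.

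No separate change to the 5% check is needed. With stable pre-dose levels, these changes remove the baseline distortion when one or two samples are invalid. The cost is a few sentences of analysis wording before database lock, with no operational change.
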